5. STATISTICAL METHODOLOGY

5.1. GENERAL CONSIDERATIONS

Continuous data will be described by the number of observations (N), the number of missing observations (Nmiss), mean, SD, median, minimum (min), and maximum (max). Categorical data will be described by the number (n) and percentage (%) of patients in each category. Missing and invalid observations will be tabulated as separate categories. The calculation of proportions will not include the missing/invalid category.

Statistical comparisons will be made using two-sided tests at the $\alpha = 0.05$ significance level unless stated otherwise. Due to the exploratory nature of the analyses, adjustments for multiple comparisons will not be made.

Unless otherwise specified, all summaries will be presented by treatment group.

5.2. PATIENT DISPOSITION

Patient disposition is included in the clinical SAP and will not be repeated herein.

5.3. PRO COMPLETION

Instrument completion rate at each timepoint will be reported for each instrument on the ITT population. The following will be provided:

- The number of patients expected to complete a PRO assessment at each timepoint
- Unadjusted completion rate at each timepoint will be calculated as the number of patients meeting at least the minimum requirements for scoring of the instrument divided by the number of patients in the ITT population.
- Adjusted completion rate at each timepoint will be calculated as the number of patients meeting at least the minimum requirements for scoring of the instrument divided by the number of patients who are expected to have PRO assessments.

A patient is expected to complete the PRO instrument as long as the patient is still on treatment and has not discontinued the study.

The minimum requirements for scoring the instruments is as follows:

- CARES: at least 50% of items are answered (e.g. 10 out of the 19 items)
- PROMIS: all 16 items are answered
- SF-36: at least one domain can be calculated
- EQ-5D: at least one item is answered
- PGIC and PGIS: item answered

Document: \\ieedc-vnasc01\Sites\[\NLHOF\IntProjects\Consulting\Projects\Corvidia\Biostatistics\01.Documentation\02.SAPI\Corvidia_RESCUE_PROSAP_v2.0_21JUL2020
Author: \[REDACTED] Version No: v.2.0
Template No.: \[REDACTED] Version Date: 21JUL2020
Effective Date: 01Dec2018 Reference: \[REDACTED]

Copyright © 2018 \[REDACTED] All rights reserved. The contents of this document are confidential and proprietary to \[REDACTED] and its subsidiaries. Unauthorized use, disclosure or reproduction is strictly prohibited.

The completion rates by treatment group at each analysis visit will also be provided graphically by means of a line graph.

5.4. DEMOGRAPHICS AND BASELINE CHARACTERISTICS

Demographics and baseline characteristics are included in the clinical SAP and will not be repeated herein.

5.5. DESCRIPTIVE ANALYSES

5.5.1. ITEM LEVEL

For all items from the following instruments :CARES, PROMIS Fatigue Short Form 13a and selected items from the PROMIS Item Bank and PROMIS interest in sexual activity item, EQ-5D-5L, PGIS and PGIC, the following will be provided:

- A table with the distribution of response by treatment group for each analysis visit

For the PGIS, a table with the distribution of change in response categories (as defined in section 4.2.5) by treatment group for each analysis visit.

In addition, the following graphical representations will be provided:

- A stacked column chart of the distribution of response by treatment group at each analysis visit
- For the PGIS, a stacked column chart of the distribution of change in response categories (as defined in section 4.2.5) by treatment group.

5.5.2. DOMAIN AND OVERALL SCORE LEVEL

The following domain and overall scores will be analysed:

- CARES: TSS and all other potential subscales resulting from the psychometric analysis
- PROMIS Fatigue: total, symptoms and impact domains from the 13-item set, as well as other potential subscales resulting from the psychometric analysis
- SF-36:
 - Domains: PF, RP, BP, GH, VT, SF, RE and MH
 - Summary scores: PCS and MCS
- EQ-5D-5L: VAS and utility index

The following analyses will be presented on the ITT population:

- A table with descriptive statistics for the PRO scores and a line graph with mean values and corresponding 95% CI will be presented by treatment group and each PRO assessment

Document: \\ieedc-vnasc01\Sites\ [REDACTED]\NLHOF\IntProjects\Consulting\Projects\ Corvidia\ [REDACTED]
Biostatistics\01.Documentation\02.SAPI Corvidia_RESCUE_PROSAP_v2.0_21JUL2020
Author: [REDACTED] Version No: v.2.0
Template No.: [REDACTED] Version Date: 21JUL2020
Effective Date: 01Dec2018 Reference: [REDACTED]

- A table with descriptive statistics for the change from baseline in PRO scores will be presented by treatment group and each post-baseline PRO assessment
- A table showing the proportion of patients achieving $\geq 0\%$, 10%, 20%, 30%, 40%, 50% and 60% percentage change from baseline during the study will be presented by treatment group. Bar plots depicting the same proportions by treatment group will be created separately for each time point during the study
- A CDF plot showing a continuous plot of the absolute change from baseline during the study for the PRO scores on the X-axis and the cumulative percent of patients experiencing that change on the Y-axis will be presented by treatment group and each PRO assessment

5.6. LONGITUDINAL ANALYSIS OF CHANGE FROM BASELINE

Change from baseline to Week 13 and Week 24 in PRO scores will be analyzed using a restricted maximum likelihood (REML)-based repeated measures approach (MMRM – Mixed Model Repeated Measures) (Brown & Prescott, 2006) as described in the clinical SAP.

The MMRM assumes that the missing observations are missing at random (MAR). That is, MMRM assumes that, given the statistical model and given the observed values of the outcome, missingness is independent of the unobserved values. A corollary is that MAR assumes that a subject's missing values can be estimated based on similar subjects who remained in the study. This infers that withdrawals (who may not receive study medication) have similar symptoms to some who continue to be treated. Given the expectation that PRO scores could be lower (poorer quality of life and/or more disease-related symptoms) after discontinuing the study medication, the MAR's assumption of the similarity of withdrawals and those who stay in the study may not be realistic for all subjects. To address the possibility of the data being missing not at random (MNAR) (e.g., non-ignorable missing data), a second analysis may be implemented using a PMM with sequential modelling with multiple imputation using placebo-based imputation (O'Kelly & Ratitch, 2014), depending on the amount of missing data at each visit. Further details on this exploration can be found in Section 5.9.2. The PMM will be used to assess the robustness of the MMRM estimate with regard to missing data when the MAR assumption is replaced by assumptions that are likely to be relatively less favorable to the experimental treatment. Due to the impact of the Coronavirus Disease 2019 (COVID19) pandemic on the RESCUE clinical trial, an immediate discontinuation of dosing was announced on March 18, 2020 to ensure the safety of trial patients. Therefore it is expected that a large number of patients will not have data at Week 24.

Analyses included in the clinical SAP will not be repeated here. The analyses will be performed on the ITT population and for each of the following PRO scores:

- CARES: TSS and other potential subscales resulting from the psychometric analysis
- PROMIS Fatigue: total, symptoms and impact domain from the 13-item set, as well as other potential subscales resulting from the psychometric analysis
- SF-36:

Document: \\eedc-vnasc01\Sites\[\redacted\]\NLHOF\IntProjects\Consulting\Projects\Corvidia\Biostatistics\01.Documentation\02.SAP\ Corvidia_RESCUE_PROSAP_v2.0_21JUL2020
Author: \redacted Version No: v.2.0
Template No.: \redacted Version Date: 21JUL2020
Effective Date: 01Dec2018 Reference: \redacted

- Domains: PF, RP, BP, GH, VT, SF, RE and MH
- EQ-5D-5L: VAS and utility index.

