1.1. OBJECTIVES OF THE PRO ANALYSIS

The aim of PRO analysis is to assess the benefits of ziltivekimab compared to placebo on disease-related symptoms, pain, and health related quality of life (HRQoL) in adult subjects with Stage 3-5 Chronic Kidney Disease (CKD).

Key objectives of the PRO analyses are:

- To assess the impact of ziltivekimab vs. placebo on symptoms (collected in Corvidia ePRO (CARES), Patient-Reported Outcomes Measurement Information System (PROMIS®) Fatigue Short Form 13a and selected items from the PROMIS Item Bank) as measured by mean changes from baseline to Week 13 and Week 24.

Supportive objectives are:

- To assess the time to first clinically meaningful deterioration, as well as time to definitive clinically meaningful deterioration, in symptoms as measured by CARES, PROMIS Fatigue Short Form 13a and selected items from the PROMIS Item Bank.
- To assess responder proportions at Week 13 and Week 24 in symptoms as measured by CARES, PROMIS Fatigue Short Form 13a and selected items from the PROMIS Item Bank.
- To examine the range of the responder definitions by looking into the Cumulative Distribution Function (CDF) plots of ziltivekimab vs placebo.

Document: \\ieedc-vnasc01\Sites\ [REDACTED]\NLHOF\IntProjects\Consulting\Projects\ Corvidia\ [REDACTED]\Biostatistics\01.Documentation\02.SAP\ Corvidia_RESCUE_PROSAP_v2.0_21JUL2020
Author: [REDACTED] Version No: v.2.0
Template No.: [REDACTED] Version Date: 21JUL2020
Effective Date: 01Dec2018 Reference: [REDACTED]

- To assess the impact of ziltivekimab vs. placebo on functioning and HRQoL as measured by mean changes from baseline at Week 13 and Week 24 on physical and mental component scores as collected in SF-36, as well as on overall HRQoL, as measured by the EQ-5D-5L.

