- Difference in change in TIBC from Baseline to Week 13 and to End of Treatment (Weeks 23 through 24) between each active group and placebo.
- Difference in change in serum ferritin from Baseline to Week 13 and to End of Treatment (Weeks 23 through 24) between each active group and placebo.
- Difference in change in serum iron from Baseline to Week 13 and to End of Treatment (Weeks 23 through 24) between each active group and placebo.
- Difference in change in serum hepcidin from Baseline to Weeks 13 and to End of Treatment (Week 24) between each active group and placebo.
- Difference in percent change in serum NT-pro-BNP from Baseline to Week 13 and to End of Treatment (Weeks 23 through 24) between each active group and placebo in patients with baseline NT-pro-BNP > 250 pg/mL.
- Difference in change in hemoglobin from Baseline (average of the two most recent hemoglobin values prior to randomization and Day 1) to Week 13 and to End of Treatment (Weeks 23 through 24) between each active group and placebo in patients with baseline hemoglobin < 11 g/dL.
- Difference in change in serum albumin from Baseline (average of the two most recent serum albumin values prior to randomization and Day 1) to Week 13 and to End of Treatment (Weeks 23 through 24) between each active group and placebo in patients with baseline albumin < 4.0 g/dL.

For the above efficacy variables, the observed values, changes from baseline, and percent changes from baseline (as applicable) will be summarized by treatment group using descriptive statistics using ITT.

For PROMIS fatigue 13a short form, the observed value and change from baseline in total fatigue score will be summarized by treatment at each visit.

For PROMIS SexFS, the observed value and the change from baseline will be summarized by treatment at each visit..

The PCS, MCS, and domain scores from the Optum SF-36 v2® Health Survey will only be analyzed descriptively. The observed value and change from baseline in total Optum SF-36 v2® Health Survey score will be summarized by treatment at each visit.

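### SF-36 PCS and MCS, named in the PRO objective, are missing from the PRO SAP's MMRM list, and the clinical SAP contradicts itself on whether they are compared with placebo

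*SAP*

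**What the plan says.** **PRO SAP v2.0.** The last supportive objective in section 1.1 is to assess ziltivekimab against placebo through "mean changes from baseline at Week 13 and Week 24 on physical and mental component scores as collected in SF-36", together with overall HRQoL measured by the EQ-5D-5L. Section 4.2.3 derives the SF-36 scales, PCS and MCS. The descriptive section, 5.5.2, lists the eight domains and adds "Summary scores: PCS and MCS". The MMRM section, 5.6, lists for SF-36 only "Domains: PF, RP, BP, GH, VT, SF, RE and MH", followed by the EQ-5D-5L VAS and utility index. It also states: "Analyses included in the clinical SAP will not be repeated here".

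**Clinical SAP (31 March 2020).** Sections 2.3.3 and 3.4.3 list, as an exploratory endpoint, the difference from placebo for each dose in change in PCS, MCS and the domain scores, at Week 13 and End of Treatment. Section 3.4.3 opens by treating continuous exploratory endpoints as the primary endpoint is treated. Further down, the same section says: "The PCS, MCS, and domain scores from the Optum SF-36 v2® Health Survey will only be analyzed descriptively". The next sentence reads: "The observed value and change from baseline in total Optum SF-36 v2® Health Survey score will be summarized by treatment at each visit". Section 3.4.3 ends by leaving additional inferential statistics for SF-36 and its derived scores to the PRO SAP. Section 5, on the COVID-19 stop, assigns MMRM to exploratory endpoints at Week 13 and ANCOVA to End of Treatment.

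**The concern.** The two SF-36 scores that the objective names are the two that the inferential list leaves out. A reader who turns to the clinical SAP for the missing analysis finds one statement that provides it and another that withdraws it. If the SF-36-specific restriction is followed, the PCS and MCS part of the objective gets tables of mean change by arm but no LS mean difference, confidence interval or p-value, while the eight domains, which the objective does not name, get all three.

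The PRO SAP makes no multiplicity adjustment (section 5.1). Leaving the analysis of the two named scores open therefore allows the choice to be made after results are known, which defeats the pre-specification that the plan sets as its purpose. Separately, the 'total' SF-36 table cannot be programmed, because no such score is derived.

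**Working it through.** The plan states no figure on this point, so the check sets the texts side by side and adds one count.

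**1. Is the omission real or a text-extraction effect?** In v2.0 the section 5.6 list runs across a page break. PRO SAP v1.0 (22 April 2020), section 5.6, has the same list without a break inside the SF-36 bullet, and it also stops at the eight domains. The omission is real.

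**2. Is there another inferential route in the PRO SAP?** Responder analysis (5.7) and time to event (5.8) cover only CARES and PROMIS Fatigue. Section 5.6 is the only between-group model there for SF-36.

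**3. Does the non-repetition clause explain the omission?** It would if the clinical SAP analysed PCS and MCS but not the domains. The clinical SAP instead treats all three together, both in the exploratory endpoint and in the descriptive-only sentence. A clause that removed PCS and MCS would remove the domains as well, yet they stay in 5.6. The EQ-5D-5L index, also an exploratory endpoint of the clinical SAP, stays too. The clause does not consistently account for the gap.

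**4. What does the clinical SAP specify for PCS and MCS?**

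| Place in clinical SAP | Treatment of PCS and MCS |
|---|---|
| 2.3.3 and the list in 3.4.3 | Difference in change from placebo, each dose |
| Opening of 3.4.3 | As the primary analysis (3.4.1: MMRM with LS mean differences, CIs, p-values) |
| 3.4.3, after the list | Descriptive only |
| 3.4.3, closing paragraph | Additional inference left to the PRO SAP |
| Section 5 | MMRM at Week 13, ANCOVA at End of Treatment |

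The third row conflicts with the first, second and fifth. The fourth sends the reader to a PRO SAP list that lacks the two scores.

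**5. Is a 'total' SF-36 score defined?** Clinical SAP 2.3.4.3 describes eight scales plus physical and mental summary scores. PRO SAP 4.2.3 derives the scales (including the health transition item), PCS and MCS. Neither gives a total.

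**6. Count within PRO SAP 5.6, per visit.** Domains: 8 scores x 3 doses = 24 contrasts with placebo. PCS and MCS: 2 x 3 = 6 would answer the objective, and 0 of them are listed. Over Week 13 and Week 24 that is 6 x 2 = 12. This counts section 5.6 alone; it does not count what the clinical SAP might supply.

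**The case against.** The strongest reply is that a between-group analysis of PCS and MCS does exist in the clinical SAP: they are in its exploratory list, that list follows the primary method, and section 5 names the models for Week 13 and End of Treatment. The descriptive-only sentence can be read as limiting what the clinical SAP reports, with inference passed to the PRO SAP a few lines later. On that reading what remains is one missing line in 5.6. The same objective also covers the EQ-5D-5L, which is in the MMRM list, and the domain scores belong to the same exploratory endpoint as PCS and MCS, so their 24 contrasts are not irrelevant. All of this is supportive or exploratory.

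Much of this stands. A reader might infer from section 5.6 and the descriptive-only sentence that the objective has no between-group test at all, and that 0 of 6 contrasts are planned anywhere. The documents do not support that: the clinical SAP's list and its section 5 point the other way, and the EQ-5D-5L part is covered.

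The reply does not remove the point. The restriction in 3.4.3 is the statement specific to SF-36, so it is the one a programmer would most naturally follow. And if inference is passed on to the PRO SAP, it arrives at a list without PCS and MCS.

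**Conclusion.** The point holds as an omission in one document and a contradiction in the other. PCS and MCS are named in PRO SAP 1.1, are absent from PRO SAP 5.6, and are both given and denied a comparison with placebo in the clinical SAP. No unambiguous between-group analysis of them is specified. Only if the descriptive-only sentence governs do they get no between-group estimate, CI or p-value; that is an assumption about precedence which the documents do not settle. The 'total' SF-36 score is undefined on any reading.

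The reach is limited to the SF-36 summary-score part of one supportive objective. The EQ-5D-5L part, the primary hs-CRP result and the secondary endpoints are unaffected. It should be corrected because it is cheap and the plan cannot otherwise be shown to answer its own objective.

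**What to change.** 1. **PRO SAP 5.6:** add "Summary scores: PCS and MCS" to the SF-36 bullet, as in 5.5.2. This brings the two scores into the MMRM and, where it is run, the pattern-mixture sensitivity analysis.
2. **Clinical SAP 3.4.3:** replace the descriptive-only sentence with one stating that the between-group analysis of PCS, MCS and the domain scores is the PRO SAP 5.6 model. Make it agree with the exploratory list and opening of 3.4.3, with its closing hand-over, and with section 5.
3. **Week 24 / End of Treatment:** say which analysis applies. Clinical SAP section 5 doubts MMRM for End of Treatment and uses ANCOVA, whereas PRO SAP 5.6 puts Week 24 in the MMRM. The timepoints also differ. PRO SAP 4.2.3 uses the Week 23 and Week 24 mean, or the single one available. The clinical SAP addendum (section 2.3) lets the last assessment after Week 13, or Week 13 itself, stand in for patients stopped by COVID-19. Without this step, adding PCS and MCS to 5.6 would leave them with two competing models.
4. **'Total' SF-36 sentence in clinical SAP 3.4.3:** delete it, or replace the total with PCS, MCS and domain scores.

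If description only was intended, the alternative is to amend PRO SAP 1.1 and the clinical SAP's exploratory list and methods to say so. Presenting PCS and MCS ahead of the domains is optional.

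Cost: a few lines across the two plans and two more model fits. The scores are already derived, and no new data are needed.

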5.6.1. MMRM

All PRO assessments will be included for this analysis. The analysis will be based on observed data, i.e., data collected at each timepoint without carrying forward previous values. Data from a limited number of PRO assessments may be used in case of substantial dropout (i.e., analysis will be limited to timepoints at which at least 10% of patients have non-missing data in both treatment groups).

The response variable will be the change from baseline to each PRO assessment. The model will include the treatment arm (ziltivekimab vs. placebo) and timepoint (Week 5, Week 13, and week 24) as fixed-effect categorical factors, the baseline PRO score and stratification factors (baseline haemoglobin (≥ 11 or < 11 g/dL) and CKD stage (3, 4 or 5)), as well as the baseline PRO score x time and treatment x time interactions. Both main effects and the interaction terms will remain in the model, regardless of significance. The model will present least squares (LS) mean estimates for each dose, least squares mean differences of each study drug dose from placebo, standard errors, 95% CIs and p-values (where applicable) for mean changes from baseline to each visit. A plot of the LS means accompanied by the 95% CI will be produced.

In addition, an overall adjusted mean estimate will be derived that will estimate the average change from baseline across all time points, giving each visit equal weight.

The standardized mean difference (SMD) including 95% CI (Hedges' g) will also be provided.

The MMRM analysis will be conducted using PROC MIXED in SAS. The model will assume unstructured covariance among the within-patient repeated measurements. If the algorithm does not converge, a heterogeneous Toeplitz (the TOEPH option in SAS PROC MIXED) will be tried first and then AR(1) as a covariance structure to achieve convergence. The Kenward-Roger approximation will be used to estimate denominator degrees of freedom.

Variables listed as categorical in the list above will be included in the CLASS statement of the procedure. The unique patient identifier will also be included as a class variable. A REPEATED statement over the visits will be included with the unique patient identifier as the SUBJECT variable in the REPEATED statement.

The normality and homoscedasticity of the residuals will be visually checked. Particularly, the scatter plot of the residuals versus the predicted endpoint values, the histograms, and the normal probability plots of the residuals will be reviewed. Transformation of the raw data will be considered if needed.

5.6.2. PMM

Change from baseline in PRO domain and overall scores may be further analyzed using a pattern-mixture model using sequential modelling with multiple imputation as described by O'Kelly (O'Kelly & Ratitch, 2014), depending on exploration of the amount of missing data at post-baseline assessments, as described in Section 5.9.2.

Document: \\ieedc-vnasc01\Sites\[\]\NLHOF\IntProjects\Consulting\Projects\Corvidia\[\]
Biostatistics\01.Documentation\02.SAPI Corvidia_RESCUE_PROSAP_v2.0_21JUL2020
Author: \[\] Version No: v.2.0
Template No.: \[\] Version Date: 21JUL2020
Effective Date: 01Dec2018 Reference: \[\]

The results from this analysis will be used to judge the validity of the MAR assumption. Similar conclusions from MMRM and PMM would suggest that the results are not overly dependent on the assumptions of the primary analysis with regard to the missing data.

The sensitivity analysis will consider dropout reasons while imputing missing values after the discontinuation. Subjects who discontinued due to lack of efficacy or adverse events in the active arms are assumed to have no treatment effect after the discontinuation. These subjects are assumed to copy the profile in the placebo arm, and missing values are imputed based on the distribution estimated from the placebo group under the missing not at random (MNAR), using copy-reference approach. The rest of missing values in the placebo arm and active arms will be imputed using the observed data in their respective group under the MAR assumption. This includes the patients who were early terminated due to the impact of the Coronavirus Disease 2019 (COVID19) pandemic. The multiple imputation model will include factors such as treatment arm, baseline hemoglobin category, and CKD stage, in addition to the data outcomes at each visit.

The following steps will be performed:

Step 1 Intermittent (non-monotone) missing data will be imputed using the MCMC option of SAS PROC MI (using seed=5414).

Step 2 For monotone missing data, the values for each pattern will be imputed via the chained equation method with range restriction, using SAS PROC MI option MONOTONE REG () .

Under step 2, missing values for subjects who discontinued due to lack of efficacy or adverse events will be imputed under MNAR assumption using copy-reference approach, and missing values for subjects who discontinued due to reasons other than lack of efficacy or adverse events will be imputed under the MAR assumption.

These two steps will be carried out sequentially to construct 100 hypothetical complete data sets.

An analysis of covariance (ANCOVA) model (not repeated measures, and with no random effects) with the following covariates will be performed for each imputation using the SAS Mixed procedure:

- HGB = Baseline Hemoglobin category (≥ 11 or < 11 g/dL)
- CKD = CKD Stage (3, or 4/5)
- TRT = Treatment group
- BASE = Baseline hemoglobin value

The SAS MIAnalyze procedure will be used to combine the results of these analyses for the imputations. The overall least square means, standard errors, 95% CI, and p-values will be reported.

Reasons for subject discontinuation that are identified as lack of efficacy will be discussed and finalized prior to database lock.

Document: \\ieedc-vnasc01\Sites\[\NLHOF\IntProjects\Consulting\Projects\Corvidia\Biostatistics\01.Documentation\02.SAPI\Corvidia_RESCUE_PROSAP_v2.0_21JUL2020
Author: \[REDACTED] Version No: v.2.0
Template No.: \[REDACTED] Version Date: 21JUL2020
Effective Date: 01Dec2018 Reference: \[REDACTED]

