1. INTRODUCTION

This document describes the rules and conventions to be used in the presentation and analysis of patient-reported outcomes (PRO) data collected in the COR-001-02 study. It describes the data to be summarized and analyzed, including specifics of the statistical analyses to be performed. It is intended to ensure the credibility of the study PRO results by pre-specifying the statistical approaches for the analysis of PRO data prior to database lock.

This statistical analysis plan (SAP) is based on protocol version amendment 5 dated 23 December 2019.

This plan may be revised during the study to accommodate protocol amendments and/or to make changes to adapt to unexpected issues in study execution and/or data that affect planned analyses. The final plan, if revised, will document all changes and be issued prior to database lock.

Due to the impact of the Coronavirus Disease 2019 (COVID19) pandemic on the RESCUE clinical trial, an immediate discontinuation of dosing was announced on March 18, 2020 to ensure the safety of trial patients. The announcement required the early termination visit to be scheduled as early as possible for ongoing patients followed by their entry into the safety follow-up period.

At the time of discontinuation of the study, approximately 140 patients had completed the 24-week treatment period and more than 120 patients were non-completers of the treatment period.

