2.2. SAMPLE SIZE

The primary efficacy endpoint is percent change from baseline in hs-CRP (average of the hs-CRP value prior to randomization and Day 1) to Week 13 between each active group and placebo.

Based on the observed treatment difference in percent change from baseline in hs-CRP of

Document: \\ieedc-vnasc01\Sites\ [REDACTED]\NLHOF\IntProjects\Consulting\Projects\ Corvidia\ [REDACTED]
Biostatistics\01.Documentation\02.SAPI Corvidia_RESCUE_PROSAP_v2.0_21JUL2020
Author: [REDACTED] Version No: v.2.0
Template No.: [REDACTED] Version Date: 21JUL2020
Effective Date: 01Dec2018 Reference: [REDACTED]

60.74% between combined COR-001-01 active groups and placebo and the associated pooled SD of 16.893% in hs-CRP at Week 4 from the final analysis of study COR-001-SC1, a sample size of 54 per group yields more than 99% power with 2-sided alpha=0.05.

Taking into consideration the dropout rate of 10% by the end of the study, a sample size of 60 per group is planned for this study. Accordingly, approximately 240 patients will be randomized 1:1:1:1 (60 per each treatment group) into the trial. Patient randomization will be stratified by baseline hemoglobin (≥ 11 or < 11 g/dL) and CKD stage (3, 4 or 5).

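### PRO SAP 5.6.2 reads MMRM–PMM agreement as evidence about MAR, but the PMM keeps COVID and most other missing values at MAR, so agreement is largely built in

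*SAP*

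**What the plan says.** Section 5.6 of the PRO SAP v2.0 makes the MMRM the main analysis of change to Weeks 13 and 24. It says MAR may not be realistic for everyone, because scores could worsen once study drug is stopped. It then introduces a PMM to see what happens "when the MAR assumption is replaced by assumptions that are likely to be relatively less favorable to the experimental treatment".

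Section 5.6.2 makes the PMM optional, depending on the amount of missing data. It gives the PMM this role: "The results from this analysis will be used to judge the validity of the MAR assumption". It continues: "Similar conclusions from MMRM and PMM would suggest that the results are not overly dependent on the assumptions of the primary analysis".

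The imputation rule in the same section is reason-specific. Active-arm patients who stopped for lack of efficacy or an adverse event are imputed by copy-reference from placebo. All remaining missing values, in every arm, are imputed under MAR from the patient's own group. On the dosing halt the text is explicit: "This includes the patients who were early terminated due to the impact of the Coronavirus Disease 2019 (COVID19) pandemic".

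Section 1 reports about 140 completers and that "more than 120 patients were non-completers of the treatment period".

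**The concern.** A sensitivity analysis informs about an assumption only to the extent that it changes that assumption. Here the MMRM and the PMM assume the same thing for every missing value outside one group: active-arm adverse-event and lack-of-efficacy stoppers. If, as is likely, the dosing halt produced most of the missing Week 24 data, the two results will be close because most of their content is shared.

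At stake is how the Week 24 PRO results, part of the key objective in section 1.1, are described. Followed literally, section 5.6.2 would let agreement be read as showing that those results do not depend much on how missing data are handled. In fact only a small part of the missing data would have been varied.

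**Working it through.** **The plan's own figure.** The SAP gives no figure for MMRM–PMM agreement. Its only related calculation is the sample size in section 2.2, for hs-CRP: "a sample size of 54 per group yields more than 99% power with 2-sided alpha=0.05". Standardised difference 60.74/16.893 = 3.60; noncentrality 3.60 × √(54/2) = 18.7; power is essentially 100%. With 10% dropout, 54/0.90 = 60 per group. Both reproduce. The relevant input is the planned all-cause dropout of 10%.

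**Scale of non-completion.** 120/(140 + 120) = 46%, a minimum because the text says more than 120. Planned dropout would have given 0.10 × 260 = 26. The excess is 120 − 26 = 94, or 94/120 = 78% of non-completers. Attributing that excess to the dosing halt is an inference; the SAP gives no split by reason.

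**How much of the missing data changes assumption.** Assume 46% missing at Week 24, with adverse-event and lack-of-efficacy stoppers making up 3–10% of randomised patients (the upper end is the planned all-cause dropout). In an active arm, 3/46 = 7% to 10/46 = 22% of missing values leave MAR. The other 78–93% are treated alike in both analyses.

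**How far the PMM can move the estimate.** For a constant effect, copy-reference lowers the estimate by at most (stopper share) × (effect). For a 0.5 SD effect that is 0.05 × 0.5 = 0.025 SD at a 5% share and 0.10 × 0.5 = 0.05 SD at 10%.

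**Simulation.** Four arms of 65; Weeks 5, 13 and 24; 46% missing at Week 24. The MMRM was fitted with unstructured covariance. The PMM used monotone regression imputation (100 sets), copy-reference for active-arm adverse-event and lack-of-efficacy stoppers, MAR for the rest, ANCOVA and Rubin's rules. Agreement means the same decision at two-sided 0.05 (section 5.1) for a dose against placebo at Week 24. Results for a 0.5 SD effect and correlation 0.6, 500 trials:

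| Stopper share | Agreement, PMM ANCOVA on baseline PRO score | Agreement, covariates as written | MMRM estimate | PMM estimate (baseline PRO score) |
|---|---|---|---|---|
| 5% | 95.9% | 88.8% | 0.50 | 0.48 |
| 10% | 93.1% | 85.4% | 0.50 | 0.46 |

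The MMRM was significant in about 76% of comparisons, which implies a standard error near 0.50/(1.96 + 0.70) = 0.19. The PMM shift of 0.02–0.04 SD is a tenth to a fifth of that.

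Across the settings run (effects 0–0.8 SD, shares 3–10%, correlations 0.4–0.8), agreement was about 92–100% with baseline PRO score and about 81–99% as written. As written, section 5.6.2 defines the ANCOVA's BASE term as baseline hemoglobin. The extra disagreement comes from that covariate, not from any test of MAR.

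**Does agreement respond to a departure from MAR among COVID stoppers?** On the same seeds, those active-arm patients were made to lose the whole effect and worsen by a further 0.5 SD after stopping. Agreement was unchanged (95.9% and 93.1%), because only unobserved values differ.

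**Contrast.** With copy-reference for all active-arm stoppers and ANCOVA on baseline PRO score, the estimate fell to 0.33 and agreement with the MMRM to about 54–57%. The Week 24 conclusion can therefore depend on what is assumed for the group the planned PMM leaves alone.

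**The case against.** Several points on the other side stand.

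- **MAR may be right for this group.** The halt was announced for the whole trial on one date and was not triggered by patients' symptoms. If the target is the effect had dosing continued, MAR is a natural assumption. A reader might infer from the simulation that the MMRM overstates the effect. The documents do not support that: it follows only if loss of effect after the halt counts towards the target, and the SAP does not say so.
- **Insensitivity to unobserved values is not special to this PMM.** Any analysis of observed data behaves the same way, including the run suggested below. The valid point is narrower: the planned PMM hardly varies the assumption for most of the missing data.
- **No agreement rate can be derived from the documents.** Effect, correlation and stopper share are assumed, so a single headline percentage would be unsupported.
- **Missingness is inferred.** Non-completion of treatment is not a count of missing Week 24 forms. Instruments other than CARES are also collected at early termination, and one Week 23 or 24 form suffices for PROMIS Fatigue and SF-36.
- **The wording is hedged, the PMM is optional, and the PRO analyses are exploratory.** Section 5.6 says only that MAR may fail for some patients, so a reason-specific PMM does not contradict it.

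Other parts of the plan touch on this group: mean-score plots by discontinuation category, with COVID separate (section 5.9.2), and the End of Treatment analysis from observed assessments by ANCOVA (clinical SAP section 5; addendum 2.3). They are useful, but neither varies what is assumed about unobserved Week 24 values.

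**Conclusion.** The point holds in a limited form. Agreement between the MMRM and the planned PMM cannot judge MAR. It supports robustness only to the handling of active-arm adverse-event and lack-of-efficacy stoppers, and not for the group that probably supplies most missing Week 24 data. Under the assumptions listed, the same p<0.05 decision is expected in about 92–100% of trials with baseline PRO score in the PMM ANCOVA and about 81–99% as written.

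This rests on at least 46% non-completion, an assumed 3–10% stopper share, and the inference that COVID terminations dominate. It does not show that MAR is false, that the Week 24 estimate is biased, or that the report will overclaim. For exploratory endpoints it is a worthwhile, inexpensive correction.

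**What to change.** 1. In PRO SAP section 5.6.2, delete "The results from this analysis will be used to judge the validity of the MAR assumption".
2. Limit the sentence that follows it: similar conclusions indicate robustness to the assumption made for active-arm patients who stopped for an adverse event or lack of efficacy, and to nothing wider.
3. Keep the planned PMM. If it is run, add a delta-adjusted tipping-point analysis at Week 24 on the same imputation code. Worsen all imputed active-arm values, COVID stops included, in prespecified steps (upwards for CARES and PROMIS Fatigue, downwards for SF-36 and EQ-5D). Report the delta at which the conclusion changes against the meaningful-change threshold from the psychometric analysis plan. That plan derives thresholds only for CARES and PROMIS Fatigue, so for the other scales report the delta alone.
4. Copy-reference for all active-arm stoppers may be reported as an optional supplementary analysis, not as a condition for claiming robustness.

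The cost is a wording change and one further set of imputation runs, with no new data. The downside is that the Week 24 sensitivity result may look less favourable.
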